7.0 Study Withdrawal/Discontinuation

It is anticipated that this study will be completed within the time frame proposed and that it will establish that vitamin E is beneficial in HIV infected patients with NASH. If vitamin E is found to exert beneficial effects on hepatic fat content and markers of NASH, it will justify undertaking larger multicenter randomized trials with histological end points to evaluate the efficacy and safety of vitamin E in this population.

Inability to meet target enrollment in a timely fashion is always a concern for any clinical trial. However, the sample size is realistic and enrollment is spread across several funding years and at two leading liver centers. People with cirrhosis have been excluded from this trial, as hepatic fat usually diminishes or disappears with progression to cirrhosis and will likely be difficult to measure at baseline in these patients. To minimize observer variability, MR-PDFF images will be centrally read by the study radiologist. Although concerns have emerged about increased risk for prostate cancer with vitamin E use in healthy men (144), this should be less of concern in HIV infected men who are at lower risk for prostate cancer than non-HIV infected men, possibly due to hypogonadism (145). Assuming 10% drop out rate with the clinical trial, about ten percent more subjects than needed to get the statistical power to evaluate the primary outcome will be recruited.

Vitamin E for NASH Treatment in HIV Infected Individuals

8.0 Statistical Considerations

Because host genetic factors contribute to the response to therapy, pre-therapy baseline liver expression profiles will be studied to identify expression signature that predict response to vitamin E therapy. This approach has been used in other liver disease such as hepatitis C. For example, in one study, pre-treatment peripheral blood monocytes gene expression signature predicted response to hepatitis C therapy with 94% accuracy (143).

Quantitative global gene expression analysis on fresh frozen liver tissue from subjects participating in the clinical trial will be performed. Based on prior experience, it is expected to have a portion of the liver biopsy snap frozen and available for expression analysis on a sizable proportion of the subjects (>50%) undergoing liver biopsies as part of Specific Aim 2 who are the primary source for the proposed clinical trial. As such, HumanHT-12 v4 Expression BeadChip will be used for this aim. This chip provides genome-wide transcriptional coverage of well-characterized genes and their splice variants, and targets more than 47,000 probes derived from the NCBI RefSeq Release 38 (November 7, 2009) and other sources.

After detectable transcripts are identified, expression data will be standardized. The t-test statistic will be utilized to measure the expression difference between the sample means (responders vs. non-responders) in units of the standard deviation for which the difference can be tested using certain p value. For this, a significance cut-point of $p < 0.001$ will be used. Then hierarchical clustering and gene network and pathway analysis will be performed to identify those predicting response to vitamin E therapy. A logistic multivariate-based analysis will be used to build up a receiver operating characteristic (ROC) curve, and the area under the ROC curve (AUC) will be calculated to assess the average sensitivity of the biomarker in discriminating the responders and non-responders.

All endpoints are measured as the change from baseline to 24 weeks. The primary outcome measure is the change in hepatic fat content as measured by central reading of MR-PDFF performed at baseline and end of study. Secondary endpoints will be changes in inflammatory markers (liver enzymes, TNF-alpha, IL-10 levels), serum K-18, Liver stiffness and CAP measurement by TE, and MDA level as a marker of oxidative stress.

The primary outcome is the improvement in liver fat as assessed by MR-PDFF at end of treatment compared to baseline. To our knowledge, there are no data on studying the effect of vitamin E on MR-PDFF in NASH patients with HIV. Using an alpha of 5% and a two-sample independent t-test and equal variance assumption, a sample size of 25 per group will have 91% power to detect an effect size of 0.97 and will have 80% power to detect an effect size as small as 0.81. To ensure this number is achieved, 28 subjects per group will be recruited, allowing for 10% drop-out during the trial. The primary purpose of this pilot study is to generate preliminary data to estimate the mean and variability of improvement in liver fat with vitamin E in HIV infected patients with NASH.

Primary outcomes analysis: The primary analysis will be based on an analysis of covariance (ANCOVA) to compare the improvement in liver fat due to vitamin E relative to placebo. The model will include one dummy variable for treatment group indicator as well as baseline demographic characteristics and baseline liver fat. The 95% confidence intervals for the difference between the two treatment groups will be reported.

Vitamin E for NASH Treatment in HIV Infected Individuals

Secondary outcomes analysis: Secondary efficacy end points are continuous and as such the ANCOVA model will be used as described for analyzing the primary outcome except that the model will include the baseline value of the response variable.

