A total of 56 subjects at two sites will be enrolled in this trial, with approximately 28 individuals included at IU and 28 at Massachusetts General Hospital. Subjects will be randomly assigned to either Group A or Group B.

Group A: Vitamin E (RRR alpha-tocopherol) 800 IU/daily for 24 weeks.
Group B: Matching placebo for 24 weeks.

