5. focused physical examination
6. measurement of waist and hip circumference
7. approximately 50mL of blood during a fasting state will be collected for the following tests:
 - a. liver profile
 - b. complete blood count
 - c. lipid
 - d. insulin
 - e. glucose
 - f. INR
 - g. MDA
 - h. K-18
 - i. TNF-alpha
 - j. IL-10
 - k. alpha and gamma-tocopherols
8. female subjects of child-bearing potential will have pregnancy test and the pregnancy test must be negative to participate in the study
9. a positive urine pregnancy test will be confirmed with a serum pregnancy test

Vitamin E for NASH Treatment in HIV Infected Individuals

10. transient elastography (FibroScan®) will be performed by a trained technician to measure steatosis by Controlled Attenuation Parameter (CAP) and fibrosis by liver stiffness (LSM)
11. MRI will be performed to measure hepatic fat content by PDFF according to the established protocol

Randomization

At the same visit, after the baseline evaluation is completed, subjects will be randomly assigned to either Group A: vitamin E in the form of all natural RRR-alpha tocopherol at 800 IU/d for 6 months (n = 28) or Group B: matching placebo for 6 months (n = 28). We will use a stratified randomization plan based on one factor, diabetes, similar to the recent FLINT trial (142). This will ensure two treatment groups having similar distribution of diabetes. A stratum specific computer-generated randomization list will be prepared by the study statistician to randomly assign study subjects in one of the two treatment groups. A block size of four will be used to ensure balance in number of subjects recruited in the two groups. Participants will be given sufficient drug for daily dosing and will be given detailed instructions about how to take the medicine.

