Vitamin E for NASH Treatment in HIV Infected Individuals

Principal Investigator

[name]
Indiana University School of Medicine
Department of Medicine
Division of Gastroenterology/Hepatology
[name]
[name]

Statistical Plan

NCT number: 03669133

Date of Document: September 20, 2020

Statistical Considerations

Because host genetic factors contribute to the response to therapy, pre-therapy baseline liver expression profiles will be studied to identify expression signature that predict response to vitamin E therapy. This approach has been used in other liver disease such as hepatitis C. For example, in one study, pre-treatment peripheral blood monocytes gene expression signature predicted response to hepatitis C therapy with 94% accuracy (143).

Quantitative global gene expression analysis on fresh frozen liver tissue from subjects participating in the clinical trial will be performed. Based on prior experience, it is expected to have a portion of the liver biopsy snap frozen and available for expression analysis on a sizable proportion of the subjects (>50%) undergoing liver biopsies as part of Specific Aim 2 who are the primary source for the proposed clinical trial. As such, HumanHT-12 v4 Expression BeadChip will be used for this aim. This chip provides genome-wide transcriptional coverage of well-characterized genes and their splice variants, and targets more than 47,000 probes derived from the NCBI RefSeq Release 38 (November 7, 2009) and other sources.

After detectable transcripts are identified, expression data will be standardized. The t- test statistic will be utilized to measure the expression difference between the sample means (responders vs. non-responders) in units of the standard deviation for which the difference can be tested using certain p value. For this, a significance cut-point of $p < 0.001$ will be used. Then hierarchical clustering and gene network and pathway analysis will be performed to identify those predicting response to vitamin E therapy. A logistic multivariate-based analysis will be used to build up a receiver operating characteristic (ROC) curve, and the area under the ROC curve (AUC) will be calculated to assess the average sensitivity of the biomarker in discriminating the responders and non-responders.

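### The signature search uses an ordinary per-transcript t-test; with about 14 tissue samples a moderated t-test would usually find more true transcripts at the same p<0.001, provided the data scale is also specified

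*Protocol*

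**What the plan says.** Protocol section 8.0 and the SAP carry the same text on the expression analysis. Detectable transcripts are identified and the data are standardized, by a method that is not described. Responders and non-responders are then compared: "The t-test statistic will be utilized to measure the expression difference between the sample means (responders vs. non-responders) in units of the standard deviation". The threshold follows: "For this, a significance cut-point of $p < 0.001$ will be used". Neither document mentions pooling variance information across transcripts. Transcripts that pass go on to clustering, pathway analysis and a logistic/ROC step.

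No sample size or power is given for this analysis. The only guide is that frozen tissue is expected for "a sizable proportion of the subjects (>50%) undergoing liver biopsies as part of Specific Aim 2 who are the primary source for the proposed clinical" (that is, for this study). The array "targets more than 47,000 probes" before the detection filter. The documents do not define a responder and do not say whether one arm or both enter the comparison.

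**The concern.** An ordinary t-test divides each transcript's mean difference by an SD estimated from that transcript alone. With few samples that SD is imprecise, and the critical value at p<0.001 is high to allow for it. The other transcripts on the same arrays carry information on what a typical variance is, and a moderated t-test uses it by shrinking each variance toward a common value. Where samples are few this recovers power at no cost in false positives. At stake is the number of true predictors that survive the cut, since a transcript missed here is lost to every later step. The trial's endpoints are not affected.

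**Working it through.** **The plan's own power figures.** These concern MR-PDFF only, but they confirm the convention. A two-sided two-sample t-test with 25 per group at alpha 0.05 (noncentral t) gives 91.9% at 0.97 SD (stated 91%) and 80.1% at 0.81 SD (stated 80%). Also 25/(1 - 0.10) = 27.8, rounded up to 28.

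**Sample counts.** Protocol section 2.0: "A total of 56 subjects at two sites will be enrolled in this trial". Section 4.0 puts 28 in the vitamin E arm. At the 50% floor:
- vitamin E arm only: 0.5 x 28 = 14 samples, df = 12;
- both arms: 0.5 x 56 = 28 samples, df = 26.

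**Ordinary t-test at two-sided p<0.001** (sidedness is not stated; two-sided assumed). The relative SD of a variance estimate is sqrt(2/df).

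| Split | df | sqrt(2/df) | Critical t | Power at 0.97 SD | 1.5 SD | 2.0 SD |
|---|---|---|---|---|---|---|
| 7 v 7 | 12 | 41% | 4.32 | 0.03 | 0.14 | 0.36 |
| 14 v 14 | 26 | 28% | 3.71 | 0.16 | 0.61 | 0.93 |

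**Moderated t-test.** With prior degrees of freedom d0 and prior variance s0², both estimated from the data, the variance becomes (d0·s0² + df·s²)/(d0 + df), and the statistic is referred to t on d0 + df. Simulated with 20,000 transcripts, 1,000 truly different, and the difference fixed in SD units, the share of true transcripts found (ordinary to moderated) is:

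| d0 | 7 v 7, 2.0 SD | 14 v 14, 1.5 SD |
|---|---|---|
| 3 | 0.369 to 0.424 | 0.601 to 0.619 |
| 5 | 0.359 to 0.442 | 0.611 to 0.637 |
| 10 | 0.355 to 0.491 | 0.607 to 0.649 |
| 30 | 0.367 to 0.587 | 0.607 to 0.687 |

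Over all cases run, the moderated/ordinary ratio was 1.15-1.81 at 14 samples (including a 4 v 10 split), 1.03-1.19 at 28 and 1.00-1.05 at 56. The upper ends come from d0 = 30, where transcript variances are nearly equal. The false-positive rate stayed near 0.001 for both tests.

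**Mixed effects.** With 15,000 detectable transcripts, 300 of them true, effects normal with SD 1.5 in own-SD units, and d0 of 4 to 10:
- 7 v 7: true transcripts found rise from 51-54 to 59-66 (15-24% more). A repeat gave 13-26%.
- 4 v 10: from 41-42 to 48-53 (14-28% more).
- 14 v 14: 2-4% more.
- False positives at 7 v 7: about 14-16 under either test, as expected from 14,700 x 0.001 = 14.7.

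**Constant fold changes** (effect fixed in raw units). At 7 v 7, power changes by +4 to +11 points at 2 SD and by -0.3 to -1.4 points at 1 SD. With mixed effects, 46-49 found rises to 49-61. Over the fixed-effect cases the ratio was 0.95-1.67 at 14 samples and 0.98-1.16 at 28.

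**If standardized means per-transcript z-scoring.** Every transcript then has total sum of squares n - 1, so all variances look alike and the estimated d0 is infinite. The moderated test uses one common variance of about 1 and a normal critical value of 3.29. The share of a transcript's variance that group membership must explain to pass is then:
- 14 samples: moderated 3.29²/13 = 0.83; ordinary 4.32²/(4.32² + 12) = 0.61.
- 28 samples: moderated 3.29²/27 = 0.40; ordinary 3.71²/(3.71² + 26) = 0.35.

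Simulation agrees. Moderated power is 0.005 against 0.36 for the ordinary test (7 v 7, 2.0 SD), and 0.43 against 0.60 (14 v 14, 1.5 SD). The two tests then rank transcripts identically.

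**The case against.** The strongest case against acting is that this is a preference about efficiency. The ordinary t-test holds its level. The signature is not a listed endpoint, and the stated primary purpose of the pilot is to estimate the mean and variability of liver-fat improvement. That stands, and it sets the grade of the point.

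The counts are also soft. The 50% is a floor, and it is stated for the Specific Aim 2 biopsy group, not for randomised patients. The text refers to tissue from trial participants without restricting the arm; if both arms are used, the floor is 28 samples and most of the gain goes. That stands too. In the other direction, the stated aim is to predict response to vitamin E, which makes a treated-arm analysis natural, and the assumed 10% drop-out would remove some patients who could otherwise be classed on week-24 MR-PDFF.

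A reader might infer three stronger things that are not supported:
- That the planned test is invalid or lets in more false transcripts. Its per-transcript rate is about 0.001 either way.
- That moderation helps across the whole range of possible sample counts. It is worth little at 28 or more, and small constant fold changes can lose slightly.
- That the ranking passed to the later steps is materially worse. The calculations count hits and do not measure ranking against the truth. The two statistics have a rank correlation of about 0.99 at 7 v 7 on unscaled data (d0 = 5).

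**Conclusion.** The point holds as a low-cost improvement to an exploratory analysis. Near 14 samples, a moderated t-test would usually find roughly 13-28% more true transcripts at p<0.001 for effects fixed in SD units, and somewhat less for constant fold changes, with false positives unchanged. At 28 or more samples the gain is generally a few percent.

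These sizes rest on assumed effect sizes, prior degrees of freedom, numbers of true and detectable transcripts, and responder splits; the documents give none of these. The gain also depends on expression values that keep their transcript-specific variances, which the plan's wording does not guarantee. Moderation does not address multiplicity (at most about 47,000 x 0.001 = 47 false positives expected before the detection filter), the undefined responder, or the unstated choice of arms.

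**What to change.** In Protocol section 8.0 and the SAP, replace the wording on standardization and on the t-test together. Suggested text: *Expression data will be log-transformed and normalised between arrays. Transcripts will not be individually z-scored, so that transcript-specific variances are kept. Responders and non-responders will be compared with a linear model per transcript and empirical-Bayes moderated t-statistics.* Keep the p<0.001 cut. Changing only the name of the test is not enough, because under per-transcript z-scoring it would do harm. If z-scoring is what the investigators intend, the ordinary t-test should stay.

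The cost is a few lines of text and a standard software call, with no new data. The method assumes that transcript variances share a common distribution, and it can lose about a point of power for small constant fold changes.

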All endpoints are measured as the change from baseline to 24 weeks. The primary outcome measure is the change in hepatic fat content as measured by central reading of MR-PDFF performed at baseline and end of study. Secondary endpoints will be changes in inflammatory markers (liver enzymes, TNF-alpha, IL-10 levels), serum K-18, Liver stiffness and CAP measurement by TE, and MDA level as a marker of oxidative stress.

The primary outcome is the improvement in liver fat as assessed by MR-PDFF at end of treatment compared to baseline. To our knowledge, there are no data on studying the effect of vitamin E on MR-PDFF in NASH patients with HIV. Using an alpha of 5% and a two-sample independent t-test and equal variance assumption, a sample size of 25 per group will have 91% power to detect an effect size of 0.97 and will have 80% power to detect an effect size as small as 0.81. To ensure this number is achieved, 28 subjects per group will be recruited, allowing for 10% drop-out during the trial. The primary purpose of this pilot study is to generate preliminary data to estimate the mean and variability of improvement in liver fat with vitamin E in HIV infected patients with NASH.

Primary outcomes analysis: The primary analysis will be based on an analysis of covariance (ANCOVA) to compare the improvement in liver fat due to vitamin E relative to placebo. The model will include one dummy variable for treatment group indicator as well as baseline demographic characteristics and baseline liver fat. The 95% confidence intervals for the difference between the two treatment groups will be reported.

Secondary outcomes analysis: Secondary efficacy end points are continuous and as such the ANCOVA model will be used as described for analyzing the primary outcome except that the model will include the baseline value of the response variable.

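### The gene-signature analysis rests on an undefined responder label; if that label splits the continuous MR-PDFF change, roughly half or more of the power per transcript is lost at 14 to 28 patients

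*Protocol*

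**What the plan says.** Protocol section 8.0 and the SAP describe the signature analysis in the same words. Each detectable transcript is tested with a t-test to "measure the expression difference between the sample means (responders vs. non-responders) in units of the standard deviation", and "a significance cut-point of $p < 0.001$ will be used". The chip "targets more than 47,000 probes derived from the NCBI RefSeq Release 38". A logistic model and ROC curve then "assess the average sensitivity of the biomarker in discriminating the responders and non-responders". Frozen tissue is expected to be "available for expression analysis on a sizable proportion of the subjects (>50%) undergoing liver biopsies" under a separate aim, which is the main source of trial participants.

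Outside this analysis, response is kept continuous. The SAP sets the general rule: "All endpoints are measured as the change from baseline to 24 weeks". On the main comparison, Protocol section 8.0 states: "The primary outcome measure is the change in hepatic fat content as measured by central reading of MR-PDFF performed at baseline and end of study", and it is analysed by ANCOVA with baseline liver fat in the model. For the remaining endpoints it adds: "Secondary efficacy end points are continuous and as such the ANCOVA model will be used".

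For the signature analysis, neither document gives:
- the variable, cut-off or time point that makes a patient a responder;
- whether the vitamin E arm alone or both arms are used;
- a sample size or power;
- a reason for working with two groups.

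**The concern.** There are two linked problems. First, an undefined label leaves the variable and the cut-off open to choice after the data are seen. Second, every candidate variable among the stated endpoints is a change from baseline. Any two-group label built from one of them treats patients just either side of the cut as opposites, and all patients on one side as alike. That discards information in the analysis that is likely to have the fewest patients and that uses the strictest threshold in the plan.

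At stake is the chance of detecting a transcript that truly tracks response. The baseline biopsy tissue is scarce and cannot be collected again once treatment has started. The estimate of the treatment effect is not at stake.

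**Working it through.** **The plan's own figure.** The only stated power is for the primary comparison: 25 per group, alpha 5%, t-test. With a noncentral t (two-sided, 48 df, noncentrality d√(25/2)), d=0.97 gives 91.9% (stated 91%) and d=0.81 gives 80.1% (stated 80%). Also 25/0.9 = 27.8, hence 28 per group. These reproduce and play no part in what follows.

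**Inputs.**
- From the documents: threshold p<0.001 (two-sided assumed); 56 randomised, 28 per arm, 25 per arm after drop-out; tissue from more than 50% of biopsied patients.
- Assumed: the label is a split of the MR-PDFF change; the split is at the median (30/70 also shown); expression and change are bivariate normal with correlation r.
- Patients with tissue: 28 × 0.5 = 14 (half of one arm); 56 × 0.5 = 28 (half of both arms, or one whole arm); 2 × 25 = 50 (all completers).

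**Large-sample information.** Splitting off a fraction f keeps φ(z_f)²/[f(1−f)] of the information:
- f=0.5: 0.1592/0.25 = 0.64
- f=0.3: 0.58
- f=0.2: 0.49

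So 36% to 51% is lost.

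**Power at p<0.001.** The continuous test is t = r√[(n−2)/(1−r²)] on n−2 df. The split test is the pooled t-test on the same simulated patients. Results are from 400,000 replicates per cell, and agree with a separate run of 100,000.

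| n | r | Continuous | Median split | Power lost |
|---|---|---|---|---|
| 14 | 0.4 | 2.2% | 0.9% | 59% |
| 14 | 0.5 | 5.5% | 1.8% | 67% |
| 14 | 0.6 | 13% | 3.5% | 74% |
| 14 | 0.7 | 30% | 6.8% | 78% |
| 14 | 0.8 | 62% | 13% | 78% |
| 28 | 0.4 | 11% | 4.1% | 63% |
| 28 | 0.5 | 28% | 9.8% | 65% |
| 28 | 0.6 | 56% | 21% | 62% |
| 28 | 0.7 | 85% | 42% | 51% |
| 28 | 0.8 | 99% | 71% | 28% |
| 50 | 0.4 | 34% | 14% | 59% |
| 50 | 0.5 | 68% | 33% | 51% |
| 50 | 0.6 | 93% | 61% | 34% |
| 50 | 0.7 | 99.6% | 88% | 12% |

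A 30/70 split is worse. At r=0.7, power is 4.6% with 14 patients and 31% with 28.

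**Error rate.** At r=0 both tests reject in about 0.1% of replicates, so the gain does not come from a looser test. Chance hits number 47,000 × 0.001 = 47 if every probe were tested and null, fewer after the detectability filter. The count is the same under either method.

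**What the t-test needs.** For 80% power the true difference must be 2.86 SD (7 v 7) or 1.74 SD (14 v 14). To pass the screen, the observed difference must exceed t_crit√(2/m), with m patients per group:
- m=7: 4.318 × √(2/7) = 2.31 SD
- m=14: 3.707 × √(2/14) = 1.40 SD

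**The case against.** **The link to MR-PDFF is inferred.** This stands. A responder could be defined on ALT, K-18, CAP or a composite. The power figures are therefore conditional on the MR-PDFF reading; the missing definition is not.

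**The loss need not be most of the power.** This stands too. A reader might infer that the split always throws away most of an already small power. The documents do not support that: they give no correlation, cut-off or number of patients for this analysis. In information terms a median split loses about 36%. With 50 patients and r=0.6 or above, or 28 patients and r=0.8, the loss is a third or less and power is not small to begin with.

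**The patient numbers may be too low.** The 50% figure is a lower bound, and the 14 further assumes that only the vitamin E arm is used. Hence the range up to 50.

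**The model favours the continuous test.** Linear bivariate normality is the setting that suits it best. With a true threshold response or gross outliers the gap would narrow.

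**Chance findings.** A reader might infer that the split is why the hit list would be mostly noise. It does not change the number of null hits; it lowers the number of true ones beside them. The multiplicity of the p<0.001 screen is a separate matter.

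**The analysis is exploratory, and an AUC needs two groups.** Both are true. The signature is not a listed endpoint, and the stated main purpose of the pilot is to estimate the mean and variability of the improvement in liver fat. That limits the weight of the point. It does not justify an undefined label or an avoidable loss in the screening step, which needs no binary outcome.

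**Conclusion.** The point holds in a limited form. It is certain from the text that the responder label is undefined and that the trial's endpoints are changes from baseline, with a continuous primary outcome. If the label is a median split of the MR-PDFF change, then with 14 to 28 patients and correlations of 0.4 to 0.7 the screen loses between 51% and 78% of its power per transcript. With more patients the loss shrinks as the correlation strengthens, to 12% at n=50 and r=0.7. These sizes rest on the assumed number of patients with tissue, the assumed correlations, the position of the cut and bivariate normality.

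The primary ANCOVA and its stated 80% and 91% power are untouched. Keeping the response continuous does not rescue the smallest case either: with 14 patients, even r=0.7 is found only 30% of the time. The change is worth making because it is cheap and the tissue is limited, but it does not bear on the validity of the trial's main result.

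**What to change.** In Protocol section 8.0 and the SAP:

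1. Name the 24-week change in MR-PDFF as the response for the signature analysis.
2. Replace the two-group t-test with a linear regression, per transcript, of that continuous change on standardised expression. Adjust for baseline MR-PDFF as the primary ANCOVA does, since baseline liver expression may track baseline fat. The p<0.001 screen can stay.
3. State how arm enters: fit in the vitamin E arm, or in both arms with an expression-by-treatment term. The first cannot separate response to vitamin E from change that would have occurred on placebo. The second can, but an interaction has less power than the table suggests; that power was not computed here.
4. Build the multivariable predictor for the continuous change and summarise it by predicted against observed change (R-squared or correlation).
5. If a responder AUC is still wanted, label it descriptive, and fix and justify its variable and cut-off in advance.

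The cost is a text amendment to both documents and a decision on arm; samples and chip are unchanged. The headline summary would no longer be an AUC, which some readers will find less familiar.

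### The exploratory expression-signature search has no stated baseline liver fat term or comparator, so it cannot tell a new predictor from a re-measurement of the baseline MRI

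*Protocol*

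**What the plan says.** Protocol section 8.0 and the SAP carry the same text on the signature search. It has three steps.

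- **Screen.** "The t-test statistic will be utilized to measure the expression difference between the sample means (responders vs. non-responders" is the selection step, and "a significance cut-point of $p < 0.001$ will be used". No covariate is named.
- **Grouping.** "Then hierarchical clustering and gene network and pathway analysis will be performed to identify those predicting response to vitamin E therapy".
- **Prediction model.** "A logistic multivariate-based analysis will be used to build up a receiver operating characteristic (ROC) curve", with the AUC as the summary. The terms in the logistic model are not listed.

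Baseline liver fat enters elsewhere: the primary ANCOVA contains the treatment indicator "as well as baseline demographic characteristics and baseline liver fat". Protocol section 4.0 schedules MR-PDFF at the randomization visit, so the value is planned for every participant.

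Three things are not stated: what makes a participant a responder (outcome, cut-off, absolute or relative scale), which arm or arms enter the signature search, and how baseline fat relates either to response or to expression.

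**The concern.** The tissue is liver and the primary outcome is change in liver fat, so expression and outcome may share a common source: how fatty the liver was at entry. If patients with more fat at baseline are more likely to be classed as responders, a transcript that merely tracks baseline fat will differ between the two groups. An unadjusted t-test cannot separate that from a transcript carrying information of its own.

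Such transcripts would also move together, because they reflect one cause. Clustering and pathway analysis could then present them as a coherent biological module. The AUC of the final model would be read without knowing what the baseline MRI achieves on its own. At stake is the interpretation of the signature: a tissue-based predictor might be reported when it repeats a measurement the trial already has. The vitamin E versus placebo comparison is not affected.

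**Working it through.** **1. The plan's own figures.** The documents give no figure for the signature search. The only sample-size figures are for the primary outcome, and they fix the available numbers. Protocol section 8.0 gives these inputs. The test is an equal-variance t-test for two groups at the 0.05 level; sidedness is not stated, and two-sided reproduces the figures. The stated power is "a sample size of 25 per group will have 91% power to detect an effect size of 0.97 and will have 80% power", the latter for a standardized difference of 0.81. On recruitment the section says "28 subjects per group will be recruited, allowing for 10% drop-out during the trial". With 25 per group the noncentrality is d × √(25/2), on 48 degrees of freedom:

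- d = 0.97: 0.97 × 3.536 = 3.43, power 91.9% (stated 91%).
- d = 0.81: 0.81 × 3.536 = 2.86, power 80.1% (stated 80%).
- Dropout: 25 / 0.90 = 27.8, rounded up to 28 per group, 56 in total.

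**2. Samples for the signature search.** The plan expects frozen tissue in more than half of those biopsied. Taking half as an assumption gives 0.5 × 28 = 14 if only the vitamin E arm is used, or 0.5 × 56 = 28 if both arms are.

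**3. Selection rate of a transcript that tracks baseline fat only.** Assumptions, none of them in the documents: normal variables; responders are the upper half of improvement; the transcript has correlation r with baseline fat; baseline fat has correlation b with improvement; and the transcript has no relation to improvement given baseline fat. The test is the t-test at p < 0.001. Simulation with 40,000 runs per setting gave:

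| r | b | n = 14 | n = 28 |
|---|---|---|---|
| 0.5 | 0.4 | 0.25% | 0.56% |
| 0.7 | 0.6 | 1.2% | 4.9% |

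Across r = 0.5–0.8 and b = 0.4–0.6 the range was 0.25% to 8.4%. With baseline fat as a covariate it was 0.08% to 0.12%.

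*Hand check at r = 0.7, b = 0.6, n = 28.* The correlation of transcript with improvement is 0.7 × 0.6 = 0.42. A median split multiplies it by √(2/π) = 0.798, giving 0.335. The noncentrality is 0.335 × √28 / √(1 − 0.335²) = 1.88, against a critical t of 3.71 on 26 degrees of freedom. The approximate selection probability is 5.5%, close to the simulated 4.9%.

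**4. When the excess disappears.** In a separate simulation (20,000 runs per setting), b = 0 gave about 0.1% throughout: no excess. Suppose proportional fat loss is independent of baseline (assumed mean loss 10% or 30%, SD 20–40%, baseline coefficient of variation 0.3 or 0.5). Baseline fat then correlates 0.07 to 0.56 with absolute improvement and 0.00 with relative improvement. The undefined scale of response therefore decides whether there is a problem.

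**5. Wider assumptions.** With b = 0.3–0.7 and r = 0.3–0.9, the rate was about 0.2% to 4.2% at n = 14 and 0.14% to 26% at n = 28. If tissue were available for all 56, it was 0.3% to 79%.

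**6. Scale of the screen.** The chip targets more than 47,000 probes. If 1,000 transcripts tracked fat (assumption), then at r = 0.7, b = 0.6, n = 28 the expected number selected is 1,000 × 0.049 = 49, against 1,000 × 0.001 = 1 with no link. At r = 0.5, b = 0.4 it is 1,000 × 0.0056 = 5.6.

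**The case against.** The strongest objection is that the stated aim is prediction. If baseline fat predicts response, a transcript that tracks fat does predict response, and insisting on adjustment changes the question and may discard transcripts that act through steatosis. This stands. It rules out making adjustment a condition for calling a transcript predictive, but it does not remove the need to show what the signature adds to a measurement already in hand.

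A reader might infer more than the documents support:

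- *That fat-tracking transcripts will be selected.* In the main settings at least 91% of such transcripts fail the threshold, and without a link between fat and response there is no excess.
- *That the plan itself treats baseline fat as related to change.* Including the baseline value is routine in ANCOVA for precision, and the secondary analyses do the same. The plan states no such relation.
- *That the logistic step omits baseline fat.* Its terms are unlisted, which is not the same as unadjusted.

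Two limits of the calculation also stand. The biopsy may precede enrollment by up to six months, while MR-PDFF is measured at the randomization visit, so a correlation of 0.7 between tissue expression and that MRI may be generous. And adjustment restores 0.1% so cleanly because the simulated transcript tracks exactly the fat value used for adjustment.

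**Conclusion.** The point holds as a conditional one. The screening test is unadjusted, and no later step states a baseline liver fat term or comparator. If responder status depends on baseline fat, transcripts that only reflect steatosis at entry may pass more often than 0.1%: about 0.25% to 8% each with 14–28 samples, under correlations of 0.5–0.8 and 0.4–0.6. Those correlations, the half-and-half responder split and the 50% tissue share are assumptions. Whether the dependence exists cannot be settled from the documents, because responder and its scale are undefined.

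What does not depend on the assumptions is that the analysis as written gives no means of separating a new predictor from a re-measurement of the baseline MRI. Severity is minor: the signature is not among the listed endpoints, the trial is a pilot whose main purpose is to estimate the mean and variability of liver fat improvement, and no efficacy conclusion rests on this analysis.

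**What to change.** Amend the signature text in Protocol section 8.0 and the SAP to:

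1. Define responder: the outcome, the cut-off, and whether change is absolute or relative.
2. Report the transcript screen with baseline MR-PDFF as a covariate alongside the unadjusted screen.
3. List the terms of the logistic model. Report the AUC of baseline MR-PDFF alone and the increment from adding the signature.
4. Claim predictive value beyond the MRI only if the signature adds to it.

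The cost is wording plus one covariate that the trial already collects. The adjusted screen uses one degree of freedom and loses precision through collinearity: at an assumed correlation of 0.7 the variance rises by 1 / (1 − 0.7²) = 1 / 0.51 = 1.96, about double. With about 14–28 samples the AUC increment will be imprecise, so it should be given with a confidence interval and described as exploratory.
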